2. ADVERSE EVENTS AND SERIOUS ADVERSE EVENTS

i. DEFINITION OF ADVERSE EVENTS

Adverse event: An unfavorable medical occurrence, which may include abnormal signs (for example, abnormal physical exam or laboratory finding), symptoms, or disease, temporally associated with, but not necessarily considered related to, the subject's participation in the research study. Not all adverse events meet IRB reporting guidelines.

Possible adverse events for this study include discomfort, invasion of privacy, and breach of confidentiality. See the DSM for greater detail.

ii. DEFINITION OF SERIOUS ADVERSE EVENTS

An adverse event or suspected adverse reaction is considered "serious" if, in the view of either the investigator or sponsor, it results in any of the following outcomes: Death, a life threatening adverse event, inpatient hospitalization or prolongation of existing hospitalization, a persistent or significant incapacity or substantial disruption of the ability to conduct normal life functions, or a congenital anomaly/ birth defect. Important medical events that may not result in death, be life-threatening, or require hospitalization may be considered serious when, based upon appropriate medical judgment, they may jeopardize the patient or subject and may require medical or surgical intervention to prevent one of the outcomes listed in this definition.

We do not anticipate any serious adverse events for this study.

iii. DEFINITION OF UNANTICIPATED PROBLEM

Any accident, experience, or outcome that meets all of the following criteria:

1. Unexpected in terms of nature, severity, or frequency;
2. Related, or possibly related, to a subject's participation in the research;
3. Places subjects or others at a greater risk of harm (including physical, psychological, economic, or social harm) than was previously known or recognized.

Possible unanticipated problems might include changes to the clinic structure based on the Covid-19 pandemic or a complaint from the subject about content of study materials.

iv. DEFINITION OF PROTOCOL DEVIATION

Non-compliance: Failure on the part of the investigator or any member of the study team to follow the terms of University of Pittsburgh IRB approved protocol or to abide by applicable

laws or regulations, or University of Pittsburgh IRB policies. This includes protocol deviations.

Incidents of non-compliance *on the part of research participants which do not involve risk* need not be reported to the IRB.

Possible protocol deviations include:

- Enrollment of an ineligible participant
- Failure to obtain consent prior to the start of study activities
- Participant interview and exit survey conducted outside of follow-up window

3. Reporting

i. General IRB Reporting Timelines for Adverse Events

Adverse Events that meet the University IRB's reporting requirements must be reported to the IRB office as follows:

- Adverse Events which are unexpected, fatal or life-threatening, and related or possibly Related to the Research Intervention will reported to the IRB within 24 hours of learning of the event.
- All other Adverse Events will be reported to the IRB within 10 working days of the investigator learning of the event.

All non-serious adverse events will be reported in aggregate to the Internal S.O. and the NIAMS as part of the routine safety report.

We do not anticipate any Serious Adverse Events such as death during this study; however, all Serious Adverse Events will be reported to the Internal S.O. and NIAMS within 48 hours of the investigator becoming aware of the event. The Internal S.O.'s feedback will be shared with NIAMS once received by the study team.

ii. *Unanticipated Problems Involving Risk to Subjects or Others and Non-compliance*

Unanticipated problems which meet the following definition of "any accident, experience or outcome" that meets all three of the following criteria must be reported:

- unexpected in terms of nature, severity, or frequency;
- related, or possibly related, to a subject's participation in the research;
- places subjects or others at a greater risk of harm (including physical, psychological, economic, or social harm) than was previously known or recognized;

Incidents of non-compliance, which meet the following must be reported:

- Failure on the part of the investigator or any member of the study team to follow the terms of University of Pittsburgh IRB approved protocol or to abide by applicable laws or regulations, or University of Pittsburgh IRB policies that:
 - adversely affect that rights and welfare of human subjects, or
 - significantly compromises the quality of the research data

3. Incidents of protocol deviations impacting participant safety:

All incidents of protocol deviation which impact participant safety will be reported to NIAMS and the Internal S.O. within 48 hours of the investigator becoming aware of the event; all other protocol deviations which do not impact participant safety can be reported as part of the routine safety report.

Examples of non-compliance that are not reportable but should be documented in a log:

- Obtaining consent using an outdated consent form when there were no substantive differences between the consent form that was used and the consent form that should have been used (i.e., dates in the footer)
- Protocol deviations that do NOT adversely affect the rights and welfare of human subjects or significantly compromise the quality of the research data
- Subject non-compliance that doesn't involve risk or alter the data
- Performing non-safety related research procedures outside the protocol specified window, i.e., involuntarily administering a questionnaire outside of the protocol specified window.

General Reporting Requirements for Unanticipated Problems Involving Risk to Human Subjects or Others and Non-Compliance:

Investigators are to submit all Unanticipated Problems Involving Risks to Human Subjects or Others that are Possibly or Definitely Related to the research and incidents of reportable Non-compliance within 10 working days of the investigator becoming aware of the reportable event/reportable new information.

L. Publication and Data Sharing Policy

This study will be conducted in accordance with the following publication and data sharing policies and regulations:

National Institutes of Health (NIH) Public Access Policy, which ensures that the public has access to the published results of NIH funded research. It requires scientists to submit final peer-reviewed journal manuscripts that arise from NIH funds to the digital archive PubMed Central upon acceptance for publication.

This study will comply with the NIH Data Sharing Policy and Policy on the Dissemination of NIH-Funded Clinical Trial Information and the Clinical Trials Registration and Results Information Submission rule. As such, this trial will be registered at ClinicalTrials.gov, and results information from this trial will be submitted to ClinicalTrials.gov. In addition, every attempt will be made to publish results in peer-reviewed journals. Data from this study may be requested from other researchers one year after the completion of the primary endpoint by contacting [name] [name]. Only de-identified data will be shared and will not be traceable back to individual participants.

M. Appendix

Screening Script

Hi Ms (_____),

Thank you again for participating in the Pitt (disease) registry. We have a new research study we wanted to tell you about. This research study is being conducted by University of Pittsburgh Division of Rheumatology and is funded by a grant from the National Institutes of Health.

The purpose of the research study is to explore whether a web-based tool called MyVoice or a pamphlet from the American College of Rheumatology helps women with autoimmune diseases to get the information and support they need to make informed decisions about if and when to have a child, and gives them information about birth control, fertility options, and how their diseases and medications might affect a pregnancy.

Does this sound like it might be of interest to you?

If No, thank the patient and hang up.

If Yes, continue

Let me tell you a little more about the research study to help you to make up your mind.

This research study will be conducted remotely. You'd need to have access to the Internet to complete this study.

Do you have access to Internet? (probe: smart phone, laptop, personal computer, tablet, etc)

If No, thank the patient and hang up.

If Yes, continue

Great. Two weeks before your next appointment with your rheumatologist, we would email or text you a link with some surveys to complete, along with either the web-based tool or a link to the pamphlet from the American College of Rheumatology. We will send you some email or text reminders to complete the study.

Overall, we think the surveys will take about 30 or 40 minutes to complete, and the tool will take about 20 minutes or so to navigate through.

Then, you'd have your visit with your rheumatologist. We'd like to interview you within a week of the visit to see how the visit with your rheumatologist went, and to give you some additional

surveys. This step would probably take an additional 30 minutes or so. We'd need to be able to talk with you over the phone. Our research coordinator will also look in your chart immediately after the visit, and 90 days after your visit.

We think altogether, you might expect to spend about two hours on the study. We would compensate you with \$40 for completing the study and \$10 to go towards your use of your cell phone minutes or data.

I should mention that your rheumatologist will not be told that you are participating in the study, and all of your survey and interview content will be kept confidential.

Might you be interested in participating in the research study? If so, I have a consent form that I will send you. If you are interested, I can go over this document with you verbally and you can consent for the study now over the phone.

If No, thank the patient and hang up.

If Yes, continue with the verbal consent.

Interview Guide

Note: Consent for participation in the study will have previously been obtained.

INTRODUCTION: (OPTIONAL)

Hello. My name is XXX. I am very appreciative that you are taking the time to talk with me today. The purpose of this research study is to hear about your thoughts and opinions related to the MyVoice:RD decision aid as well as your experiences and perspectives regarding reproductive health discussions you may have had with your rheumatologist. What we learn from talking with women like you will help us improve the tool and this aspect of care for women with rheumatic diseases.

I am going to use an audio recorder to tape our conversation. Our conversation will be entirely anonymous, which means that I won't share this recording with anyone but our study team. We will not use your name or the name of anyone else you mention in this interview.

I really want to make sure that you feel comfortable sharing your experiences and opinions with me. All questions are voluntary, so you don't have to answer any that you don't want to. You can stop participating at any time. If there are any comments or thoughts that you'd like to add, I'd love to hear them.

There are no risks or benefits to participating in this interview. I expect that the interview will take around 20-30 minutes to finish.

Do you have any additional questions about the information we just reviewed together?

If any questions do arise, please don't hesitate to ask. I'll also give you my information at the end of the interview so you can follow up with me if you wish.

Do you have any questions for me at this point?

I will turn on the recorder now.

I. MyVoice:RD Feedback

- Please tell me your thoughts about MyVoice:RD.

[Prompt] What did you like about it? What did you dislike?

[Prompt] Did you learn anything about pregnancy, parenthood, or birth control related to women with rheumatic diseases from the decision aid?

[Prompt] Has MyVoice:RD been helpful to you? Did it help you to have a conversation with your rheumatologist related to your reproductive health? Did MyVoice:RD help you make decisions related to your reproductive goals (parenthood, pregnancy, or choice of contraception)? If yes, tell me about that.

[Prompt] What can we do to make the tool better?

- Is MyVoice:RD appropriate for women with rheumatic diseases? Is it valuable?
- How usable is MyVoice:RD?

[Prompt] What features were easy to use? What features were too complex?

[Prompt] Do you need help using MyVoice:RD?

[Prompt] Were the different parts of MyVoice:RD well-integrated?

- What are the barriers to using MyVoice:RD?

[Prompt] Did using MyVoice:RD require an excessive amount of time?

- What are the facilitators to using MyVoice:RD?

[Prompt] Did anything help you to use MyVoice:RD

- Are there any situations where you think MyVoice:RD would be particularly helpful?
Are there any situations or practices where you think MyVoice:RD would not be helpful?

II. Reproductive Health Discussions with your rheumatologist

- Did you discuss your reproductive goals or plans (including parenthood, pregnancy, or choice of birth control) with your rheumatologist during your last visit? If yes, how did that discussion go? If no, why not?

[Prompt] Who initiated the conversation? Who was in the room?

[Prompt] Did you feel heard? Did your provider help you understand your reproductive decisions?

[Prompt] Did your provider listen to the things that matter most to you about your reproductive decisions?

[Prompt] How much effort was made to include what matters most to you in choosing what to do next?

- Did MyVoice:RD influence your discussions with your rheumatologist? If yes, how?
- Did you have reproductive health discussions with your rheumatologist before you used MyVoice:RD?

[Prompt] Were those conversations different at all after using MyVoice:RD?

- Do you feel confident in your ability to get answers to your reproductive health question? Seek out reproductive health care?

[Prompt] Did MyVoice:RD help at all?

N. Statistical Analysis Plan

Measures

We collected baseline information about participants' demographic and personal characteristics. Questions about contraception use, reproductive histories, and healthcare utilization were adapted from the National Survey of Growth. The Desire to Avoid Pregnancy scale was used to assess patients' preferences around a future pregnancy.

Feasibility, usability, and acceptability of MyVoice:Rheum and the control pamphlet were assessed using qualitative and quantitative measures. The validated Intervention Appropriateness Measure (IAM) and Acceptability of Intervention Measure (AIM) consist of Likert scales ranging from 1-5; we assigned a feasibility threshold of ≥ 3.5 of 5 for AIM and IAM scores, for which higher scores indicate more positive responses. Usability was assessed via summary scores from the System Usability Scale (SUS), which consists of a 10-item Likert scale with scores ranging from 0-100; we set a threshold of scores >80.3 as 'A'/excellent and 68-80.3 as 'B'/very good, consistent with standard rating for the SUS. To assess the perceived value of MyVoice:Rheum and the pamphlet, we developed a five-item Likert scale with responses ranging from 1-5 (1: strongly disagree, 5: strongly agree).

While pilot studies are not designed to test hypotheses, we preliminarily assessed the effectiveness of MyVoice:Rheum in prompting family planning discussions by comparing the incidence in which these discussions occurred across the study arms. We also evaluated self-efficacy and knowledge scores within each arm before and after the intervention. Self-reported efficacy in communicating with providers was assessed using a modified version of the validated five-item Perceived Efficacy in Patient-Provider Interactions (PEPPI) scale. Rheumatology-specific reproductive health knowledge was assessed via ReproKnow, a measure developed and preliminarily validated by our team that covers domains of contraception safety and efficacy, pregnancy management, pre-conception planning, medication safety, fertility; a score of nine indicates the highest level of reproductive knowledge. Overall knowledge scores as well as scores related to specific domains of reproductive knowledge were calculated across individuals in each study arm. Among MyVoice:Rheum users only, knowledge was assessed again three months after the intervention.

Analysis

Quantitative. Quantitative measures of demographics, feasibility, and acceptability were assessed via descriptive statistics. Among MyVoice:Rheum users and controls, we conducted paired comparisons pre- and post-intervention regarding self-efficacy and reproductive health knowledge, using McNemar's test for proportions and Wilcoxon's signed rank test for means. Calculations were performed using Stata 17.0.

Qualitative. A deductive approach was used to prepare the preliminary codebook, which was organized by the following domains: feasibility and acceptability; family planning discussed at rheumatology visit (yes/no), and reasons why or why not; barriers and facilitators to discussing family planning at the rheumatology visit; ideal timepoints and contexts to use the tool; and suggested modifications. Interview transcripts were entered into NVivo software to

facilitate coding and thematic analysis. Transcripts were reviewed by two experienced qualitative analysts with master's degrees in public health and sociology, respectively ([name], [name]). [name] and [name] used an open coding approach to identify themes that arose inductively, and subsequently refined the codebook based on the most frequent and important codes. [name], a trained research assistant, also independently coded the transcripts. As a form of investigator triangulation, the analysts and P.I. ([name]) used a consensus approach to reconcile coding and create new codes. Focus coding was used to re-review all transcripts and synthesize themes.

RESULTS

Sample Characteristics

Fifty-five patients consented to participate in the study, among whom 46 patients were randomized to a study arm. Forty patients completed the study, among whom 31 patients were randomized to the MyVoice:Rheum intervention and 9 were randomized to the control arm. The most common rheumatic disease diagnoses were SLE, RA, and myositis. Most participants identified as heterosexual, and nearly half of all participants were married. More than half of participants had at least a college degree. Over 40% of participants identified their rheumatologist as their main health provider. Most participants had never been pregnant, and approximately 10% had a diagnosis of infertility. Over two-thirds of participants used a method of contraception.

Quantitative Outcomes

MyVoice:Rheum and the control pamphlet were both rated as feasible, acceptable, usable, and valuable by study participants. The minimum threshold score of 3.5 for the Acceptability of Intervention Measure (AIM) was met or exceeded by 96.8% of MyVoice:Rheum users and 88.9% of controls; average AIM scores for MyVoice:Rheum and controls were 4.4 (S.D. 0.58) and 3.97 (S.D. 0.65), respectively. The minimum threshold score of 3.5 for the Intervention Appropriateness Measure (IAM) was met or exceeded by 96.8% of MyVoice:Rheum users and 88.% of controls; average IAM scores among MyVoice:Rheum and controls were 4.48 (S.D. 0.60) and 4.11 (S.D. 0.85), respectively. System Usability Scale scores for MyVoice:Rheum users were rated in the range of "excellent", whereas scores for pamphlet users were rated in the range of "very good" (83.0 vs. 79.3, respectively).

Approximately 55% of MyVoice:Rheum users vs. 44% of control participants discussed any family planning issues, plans, or questions with their rheumatologists during their clinic visit. Among these participants, 55% of MyVoice:Rheum users indicated that the tool influenced their decision to discuss family planning with their rheumatologists as compared to 44% of controls. Among MyVoice:Rheum users, self-efficacy scores on the PEPPI scale rose from a pre-test mean of 3.47 (S.D. 1.19) to a post-test mean 4.07 (S.D. 0.82) (mean difference: 0.59 (S.D. 0.91)).

Overall reproductive knowledge scores on ReproKnow rose from a pre-test mean of 5.77 (S.D. 1.76) to a post-test mean of 7.27 (S.D. 1.17) (mean difference: 1.50 (S.D. 1.93)). Reproductive knowledge appeared to increase across the ReproKnow domains of birth outcomes, fertility, contraception, pre-pregnancy planning, and pregnancy management.

Qualitative Outcomes. The following themes emerged from interviews with MyVoice:Rheum users: 1) MyVoice:Rheum was feasible, informative, usable, and customizable to the user; 2)

MyVoice:Rheum users felt prepared to initiate and engage in family planning conversations with their rheumatologists; 3) MyVoice:Rheum optimally should be provided for patients to review immediately prior to the rheumatology encounter, around the time of the initially RMD diagnosis and periodically afterwards; 4) Family planning conversations at the rheumatology visit were facilitated by respectful and trusting relationships with the rheumatologist, whereas distrustful relationships and rushed visits were a barrier to family planning conversations; 5) Suggested modifications to MyVoice:Rheum included tools directed towards clinicians to facilitate patient-centered care, and information modules for partners or family members. Representative quotations are presented in.

Three-month outcomes. Most MyVoice:Rheum users engaged in interviews three months following the intervention (N=30). Some MyVoice:Rheum users indicated receipt of family planning services after the intervention, including: 1) initiation of a new birth control method (N=7); 2) counseling about birth control or pregnancy planning from a clinician (N=4); and/or 3) a clinic visit or medical test related to birth control or pregnancy planning (N=3). When reproductive knowledge was re-evaluated again three months, overall scores remained significantly higher than pre-intervention scores (pre-intervention mean 5.77 (SD 1.76) vs. post-intervention 7.27 (1.17), mean difference 1.50 (1.93)).

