| Endpoints* : | Feasibility measures: 
-Number of women who express interest in the study vs who are contacted-Number of women who enroll vs. decline to participate-Completion rates for MyVoice-Technical feasibility (e.g., software reliability of MyVoice)-Number of consented women who complete the study vs. number of consented women who partially complete the study or do not open or utilize the study materials Acceptability measures: 
-Completion rates for MyVoice-Patients' satisfaction with MyVoice or pamphlet-Patients' comprehension of instructions, scales, and surveys-Completion rates for instructions, scales, and surveys Preliminary implementation measures: 
-Surveys of barriers/facilitators of use-Survey of physicians' readiness to adopt the intervention in clinic-Technical issues with video visits/Epic-Number of patients who no-show for their telemedicine visits |
| Study Population: | We will recruit 55 women aged 18-44 who are diagnosed with rheumatoid arthritis, myositis, systemic sclerosis, or systemic lupus erythematosus who receive care at one of three UPMC rheumatology clinics. Participants cannot be pregnant and cannot be sterilized. |
| Phase* or Stage: | Phase II |
| Description of Sites/Facilities Enrolling Participants: | Participants will be recruited from the UPMC Falk Rheumatology Clinic, the Lupus Center of Excellence, and the Magee Women's Health Rheumatology Clinic. |
| Description of Study Intervention/Experimental Manipulation: | Interested individuals will arrive at the clinic one hour prior to their scheduled rheumatology appointment. They will be consented and randomized to either receive the intervention (the MyVoice decision aid, an interactive website) or to receive the control pamphlet. They will have approximately 40 minutes to review the tool or pamphlet prior to meeting with their rheumatologist. |

Study Duration* : Nine months

Participant Duration: Two hours.

C. Study Flow Chart and Randomization Schema

Below is a detailed description of the data in each survey [Appendix] collected at each time point.

T0: Baseline Survey

- National Survey of Family Growth Family Planning Services Question
- COLLABORATE shared decision-making scale
- Self-efficacy (Perceived Efficacy in Patient-Provider Interactions [PEPPI])
- Reproductive knowledge (ReproKnow)
- Desire to avoid pregnancy scale (DAP)
- Demographic questionnaire

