T2: Exit Survey

- Acceptability and implementation measures for the MyVoice tool
- Reproductive knowledge (ReproKnow)
- Self-efficacy (Perceived Efficacy in Patient-Provider Interactions [PEPPI])
- Decision Conflict Scale (Low Literacy version)
- Interpersonal Quality of Family Planning (IQFP) Scale

T3: Provider Survey

- Providers' experiences with the study as well as information related to encounters with patients enrolled in the study

T4: 3 Month Survey

- National Survey of Family Growth Family Planning Services Question
- Self-efficacy (Perceived Efficacy in Patient-Provider Interactions [PEPPI])
- Reproductive knowledge (ReproKnow)
- London Measure of Unintended Pregnancy

D. Risk/Benefit Assessment

Known Potential Risks

- Discomfort- Study activities involve information regarding reproductive health; some individuals may be uncomfortable discussing this topic.
- Invasion of Privacy- Participants may feel uncomfortable discussing their reproductive health where other individuals may hear them.
- Breach of Confidentiality- Any possibility that de-identified information could be viewed by unauthorized parties.

Known Potential Benefits

- This pilot study will inform the procedures and practices related to a future full-scale testing of a patient-facing decision support tool for family planning. Our study team and others have demonstrated that women with rheumatic diseases do not receive adequate family planning care. We will not directly counsel patients about their particular risks, and therefore, patients will not receive a direct benefit from their participation. However, they may learn more about their family planning options in the context of their diseases.

Assessment of Potential Risks and Benefits

- Discomfort- We will minimize occurrence of discomfort by being clear about the content of the study tool and assessment measures during recruitment. All questions in study surveys and interviews will be optional, and participants will be told they can skip any question they do not wish to answer.
- Invasion of Privacy- The study will not be discussed with potential or current participants in public settings. Conversations about the study will only occur in private exam rooms or research spaces or via email or phone conversations. We will minimize risk by placing phone calls while in a private room and asking the potential participant whether they are in a private location before discussing the study.

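### The only between-arm effectiveness comparison, whether family planning was discussed at the visit, is not a listed endpoint and has no stated source item, time point or method; the only printed question for it follows a prompt on whether MyVoice helped the conversation

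*Combined protocol and SAP*

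**What the plan says.** - **Section N, Measures.** The plan concedes that a pilot is not built to test hypotheses. It then makes a preliminary assessment of effectiveness by "comparing the incidence in which these discussions occurred across the study arms". The other two effectiveness measures are not compared between arms: "We also evaluated self-efficacy and knowledge scores within each arm before and after the intervention".
- **Section N, Analysis, Quantitative.** The tests named are for paired pre/post data, "using McNemar's test for proportions and Wilcoxon's signed rank test for means". No between-arm method is given.
- **Protocol Summary, Endpoints.** The list covers feasibility, acceptability and preliminary implementation, for example "Survey of physicians' readiness to adopt the intervention in clinic". Occurrence of a discussion is not on it.
- **Section C, T2 exit survey.** The content is listed by heading: "Acceptability and implementation measures for the MyVoice tool", ReproKnow, PEPPI, the Decision Conflict Scale and IQFP. Item wording is not shown.
- **Section N, Analysis, Qualitative.** The only explicit yes/no definition is a codebook domain: "family planning discussed at rheumatology visit (yes/no), and reasons why or why not".
- **Appendix M, Interview Guide.** Section I, on MyVoice, includes the prompt "Did it help you to have a conversation with your rheumatologist related to your reproductive health". Section II then asks "Did you discuss your reproductive goals or plans (including parenthood, pregnancy, or choice of birth control) with your rheumatologist during your last visit". The guide refers to MyVoice throughout and has no pamphlet version.
- **Section N, Results, Quantitative Outcomes.** About 55% of MyVoice users and 44% of controls are reported to have had a discussion, without counts or an interval.

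**The concern.** This is the one figure that can be read as evidence that MyVoice works better than the pamphlet. The pilot is meant to inform a hybrid effectiveness-implementation trial, so the measure may be carried forward. A reader cannot tell which question produced it, when it was asked, or whether both arms were asked in the same words.

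The only question that can be inspected is poorly placed for a comparison. A MyVoice user is prompted on whether the tool helped her have the conversation before she is asked whether one took place. A control has no printed equivalent of that prompt. An interview built on this guide also reveals the arm to whoever codes it, and no blinding of coders is described. If the interview is the source, both features could raise the MyVoice percentage relative to the control percentage.

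**Working it through.** **1. Reproducing the reported percentages.** Section N, Results, gives 31 MyVoice and 9 control completers. With these as denominators:
- MyVoice: 17/31 = 54.8% (16/31 = 51.6% and 18/31 = 58.1% do not fit 55%).
- Control: 4/9 = 44.4% (3/9 = 33.3% and 5/9 = 55.6% do not fit 44%).

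The counts are inferred; the documents do not print them.

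**2. Precision.** Difference d = 17/31 - 4/9 = 0.548 - 0.444 = 0.104. The Newcombe interval combines the Wilson 95% limits for each arm, which are 0.378 to 0.708 (MyVoice) and 0.189 to 0.733 (control):
- Lower: 0.104 - √[(0.548 - 0.378)² + (0.733 - 0.444)²] = -0.232
- Upper: 0.104 + √[(0.708 - 0.548)² + (0.444 - 0.189)²] = 0.406

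So the difference is 10.4 points, 95% CI -23.2 to +40.6. Fisher's exact test gives p = 0.71.

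**3. How few answers carry the contrast.** One control changed from no to yes gives 5/9 = 55.6%, and the difference becomes 54.8 - 55.6 = -0.7 points from unrounded values. This shows the effect of having nine controls. It does not measure question-order bias.

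**4. How much over-reporting would be enough.** The suspected mechanism is false yes answers in the MyVoice arm. Suppose the true rate were 44.4% in both arms and a fraction f of MyVoice non-discussers answered yes. Then 0.444 + 0.556f = 0.548, so f = 0.104/0.556 = 0.19. In counts, removing three yes answers leaves 14/31 = 45.2%, within a point of the control figure. This is a what-if; the documents contain no evidence that it happened.

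**5. Where the outcome could have come from.**

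| Candidate source | For | Against |
|---|---|---|
| Interview | Only printed question; only yes/no definition; Section II also asks whether MyVoice influenced the discussion, close to the next reported result | Guide has no pamphlet wording; themes are reported for MyVoice users only |
| Exit-survey item not shown | Result sits under Quantitative Outcomes, in wording that differs from the guide; controls are included; percentages fit all completers | No such item is named in the T2 list |
| Billing code in the chart | Collected after the visit and again at 90 days | Not tied to this outcome |
| Provider survey | Asks about encounters | Anonymous, so it cannot be linked to a patient |

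The documents do not settle between the first two.

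**6. The repeated percentages.** The next sentence in the Results gives 55% vs 44% again, this time among those who had a discussion, for whether the material influenced the decision to discuss. With 17 and 4 discussers, the nearest attainable values are 9/17 = 52.9% or 10/17 = 58.8%, and 1/4 = 25% or 2/4 = 50%. Neither 55% nor 44% can occur. Either the denominator or the figures in that sentence need correcting.

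**The case against.** The strongest reply is that the source may well be the exit survey. The T2 list gives headings only. It does not name AIM, IAM or SUS either, yet Section N defines and reports them, so the absence of a discussion item from that list does not show that none was asked. The protocol places the interview after the exit survey. A survey answer would therefore precede every interview prompt and need no coder. This stands. A reader might infer that the 55% vs 44% is an unblinded analyst's code from a leading interview, and the documents do not support stating that as fact.

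Two further replies stand in part. The leading question is one prompt that may be skipped or answered no, the outcome question is factual and normally asked soon after the visit, and coding was done independently and reconciled by consensus. That limits the likely bias, but consensus is not blinding, and uneven use of a prompt does not make the arms comparable. The plan also calls the comparison preliminary, reports no between-arm test and disclaims a sample size calculation. That limits the claim, but it does not tell the reader what was measured.

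A reader might also take the one-control reversal as evidence of bias. It is not: it reflects nine controls, and it changes a control answer, whereas the suspected mechanism acts mainly in the MyVoice arm.

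**Conclusion.** The point holds in this form. The sole between-arm effectiveness comparison is not a listed endpoint and has no stated source item, time point or between-arm method. The only printed question for it comes after a prompt about MyVoice, in a guide with no pamphlet wording. Bias in the reported 55% vs 44% is possible only on the condition that the interview is the source, and the documents leave that open.

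Whatever the source, the comparison says little: 10.4 points, 95% CI about -23 to +41, assuming that completers are the denominators and that the counts are 17/31 and 4/9. The data are compatible with a sizeable difference in either direction. The repeated 55% vs 44% among discussers is unattainable with those counts, so one of the two pairs may be a reporting error.

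**What to change.** **For the follow-on trial, or for this one if any collection remains**
- Take the outcome from one fixed yes/no item, worded identically in both arms and asked at T2 before any tool-feedback items and before the interview. If such an item already exists, print it and confirm its position.
- Put Section II of the interview guide ahead of Section I, give it wording that suits either arm, and use the interview to explain the answer.

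**For the existing data, in Section N**
- State the source item, the time point and the counts (17/31 and 4/9 if the denominators are completers).
- Replace the bare percentages with the risk difference and its 95% CI (10.4 points, about -23 to +41).
- Label the comparison exploratory and not listed among the protocol's endpoints.
- Reconcile the sentence that repeats 55% vs 44% among those who had a discussion.

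**Cost.** One survey item, a reordered guide and a few sentences in Section N; the sample size does not change. The wide interval will make the result look less favourable than the two percentages alone.
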